7.1 Falls Assessment

The rate of falls will be assessed prospectively. The collection of detailed and prospective information about falls follows the recommendations of the Prevention of Falls Network Europe consensus statement (Lamb et al., 2005) and a Cochrane Collaborative review (Gillespie et al., 2012). A fall is defined as an unexpected event in which a participant comes to rest on the ground, floor, or lower level. A near fall is defined as an occasion in which a participant felt that he was going to fall but did not actually do so. Participants will be asked to record falls as they occur on monthly calendars supplied by the investigators. Also, they will be asked to record the circumstances surrounding a fall or near fall (i.e., location, time of day, direction of fall, activity being performed, presence of an environmental trigger, injuries sustained, and medical attention received).

7.2 Data Management and Security

For the purposes of this study, each patient will be assigned a unique randomly generated ID number, which will be used on all electronic data stored locally. A walk across file will be maintained to link the patient

with the random ID number and will be encrypted and stored in a separate location from all other data extracted. Only the study coordinator and PI will have access permissions to this file.

All electronic databases related to this protocol will be stored locally on a VA server in an entry controlled, locked room at the Jamaica Plain campus of the VA Boston Healthcare System. There are multiple levels of security to ensure the integrity and confidentiality of all data. The computer system operates entirely within the VA network, which is protected by a firewall maintained by the VA Office of Information Technology. Part of the maintenance of the VA server is that it is backed up regularly; therefore, all data related to this protocol will be routinely backed up and stored behind the VA firewall. Only authorized users can log on to the server. An additional layer of restrictions is at the file and directory level. Users can only access portions of the data to which they are entitled. Access to all data on the server is password protected.

All paper forms will be secured in a locked fireproof study cabinet. Only the PI will have keys to the study cabinet. All data will be kept indefinitely or until the law allows their destruction in accordance with the VA Record Control Schedule.

To minimize data entry errors, all data collected on paper forms will be entered twice by a trained staff member using software that allows specification of valid responses for each entry field. Upon second entry of each record, the software will analyze each field to check for discrepancies in the two entries. Entry errors will be corrected on the spot and any errors requiring more extensive review will be deleted and re-keyed after the errors are resolved.

8. Statistical Analysis Plan

The rate of falls over 3 months will be compared between each intervention group and the control group and between the two intervention groups, with the use of negative binomial regression models. We will base our analyses on the following model

$$\log \left[\frac{E(FALLS_i)}{t_i} \right] = a + b1.IN_PERSON + b2.REMOTE + c.CONFOUNDER \quad (1)$$

where FALLS_i is the number of falls for the ith participant over 3 months, t_i is the person-months of follow-up between the baseline exam and the 3-month exam for the ith participant, IN_PERSON and REMOTE are two dummy variables indicating that the patient was randomized to receive the in-person intervention (IN_PERSON=1, REMOTE=0), to receive the remotely-delivered intervention (IN_PERSON=0, REMOTE=1), or to the control group (IN_PERSON=0, REMOTE=0), and CONFOUNDER is a mean-centered hypothetical confounding variable. In the above model we will include an offset for the time between baseline and follow-up, which may vary slightly around the 3-month target date. **Coefficient a** estimates the log(rate of falls per month) for a control participant. The incidence rate ratio (IRR) in falls per month for a participant in the in-person exercise group vs. a participant in the control group with the same level of confounders is estimated by exp(b1). The IRR in falls per month for a participant in the remotely-delivered exercise group vs. a participant in the control group is estimated by exp(b2).

To compare the fall rates between groups, the coefficients of interest are b1 and b2. **Coefficient b1** will be tested to compare the in-person intervention vs. the control group and **coefficient b2** will be tested to compare the remotely-delivered intervention vs. the control group. Furthermore, the linear contrast b1-b2 will be tested to compare the fall rates between the in-person intervention and the remotely-delivered intervention. Specifically, exp(b1-b2) is the estimated IRR in falls per month between the in-person and remote groups.

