Identifying interventions that successfully reduce fall rate is critical to reduce disability, improve quality of life, and potentially increase survival in patients with PD. RCTs have examined the effects of exercise interventions on reducing falls in patients with PD; however, with mixed results. Evidence from two meta-analyses (Sherrington et al., 2017; Allen et al., 2011) indicates that progressive and challenging exercise programs may lead to better outcomes.

Patients with PD often have limited access to exercise programs because of distance from a center providing specialized exercise training or their inherent limited functional mobility. An evidence-based exercise program remotely delivered to the home in these patients has the potential to keep patients exercising over the long term and to reach the majority of patients regardless of geographic location or functional limitations to participating in in-person programs. In this context, approximately 34 to 36% of its enrollees live in rural areas (National Center for Veterans Analysis and Statistics, 2016; West et al., 2010). To the best of our knowledge, this will be the first RCT to compare a remotely-delivered program with an in-person program on reducing fall rate in patients with PD. Both programs incorporate the most salient features from prior work (e.g., theoretically driven, progressive, goal oriented).

4. Relevance to Veterans Health

Parkinson's disease is the second most common neurodegenerative disorder, affecting over 80,000 veterans treated within the VA Healthcare System. Falls are a major problem for many patients. A remotely-delivered home-based exercise program has the potential to be accessed easily and conveniently by large numbers of people with PD. The findings of this study may help VA clinicians provide optimal care for the many veterans with PD at risk of falls.

5. Study Design

We will conduct a three-group RCT with a 3-month intervention period and three assessment points (baseline, 3 months, and 6 months). Patients with PD will be randomly assigned to one of three interventions: in-person exercise, remotely-delivered exercise, and health education. All patients will be asked to complete 3 training sessions per week over the 3-month intervention period.

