8.1 Power

We have estimated a loss to follow-up rate of approximately 25%, i.e., ~120 of the 162 participants will finish the entire protocol. Fall rates will be compared between each exercise intervention group and the control group with the use of negative binomial regression models. Despite mixed results with exercise interventions, two RCTs have shown that in-person exercise programs reduced fall rates (61% reduction in fall rate, Morris et al., 2015; 67% reduction in fall rate, Li et al., 2012) in patients with PD. We conducted an analysis of statistical

power using the PASS program to determine the sample size needed to detect a reduction in fall rate as low as 45%. A total of 40 participants per group will be required to provide 95% power to detect a between-group difference in fall rate of 45% for a specific exercise group vs. the control group (the group receiving the in-person program vs. the control group and the group receiving the remotely-delivered program vs. the control group), each at a two-sided significance level of 0.05. We assumed the control group rate of falls would be 1.3 falls per person month (Morris et al., 2015).

9. References

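### The exam-to-exam offset leaves exposure undefined for anyone who misses the 3-month exam, so read literally the only outcome model is a completers analysis open to bias from fall-related dropout

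*Combined protocol and SAP*

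**What the plan says.** Section 8 models the fall rate by negative binomial regression. The count is defined as "FALLS_i is the number of falls for the ith participant over 3 months" and the exposure as "t_i is the person-months of follow-up between the baseline exam and the 3-month exam for the ith participant". The text adds: "we will include an offset for the time between baseline and follow-up, which may vary slightly around the 3-month target date".

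Section 7.1 gives the source of the count: "Participants will be asked to record falls as they occur on monthly calendars supplied by the investigators". It gives no schedule for returning calendars and no rule for one that is missing.

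Section 8.1 puts loss to follow-up at about 25%, so that about "120 of the 162 participants will finish the entire protocol". Section 5 shows that the protocol runs to a 6-month assessment, so this figure is not the loss before month 3, which is not stated.

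I found no analysis population, missing-data method or missing-calendar rule anywhere in the document. The telephone calls in sections 5.1 and 5.2 follow missed exercise sessions, not missing calendars.

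**The concern.** Numerator and denominator come from different sources: calendars for the falls, exam dates for the time. They agree for a participant who attends the 3-month exam with all calendars complete. For a participant who stops at month 1 or 2, the second date does not exist and t_i is undefined. Exposure that varies only slightly around 3 months does not describe such a person either.

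On that reading the primary comparison leaves out randomized participants according to something that happens after randomization. Falls, injury or worsening balance are plausible reasons to leave. If they operate differently in an exercise arm and in the education arm, the arms that remain are no longer comparable. The plan has no second analysis that would reveal this.

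A secondary gap concerns attenders with a missing calendar. The month could be recovered at the exam, treated as missing, or left out of the count while its time stays in the offset. The plan does not choose, so the choice could be made after the data are seen.

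**Working it through.** **1. The plan's own figures.** 40/(1 − 0.25) = 53.3, so 54 per arm and 162 in all (assuming equal allocation). 162 − 120 = 42 lost, or 25.9%.

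Power, from section 8.1: control rate 1.3 per month; exercise rate 0.55 × 1.3 = 0.715; 3 months; 40 per group; two-sided 0.05. The dispersion k is not stated. The variance of the log IRR is (1/3.9 + k)/40 + (1/2.145 + k)/40. At k = 0.189 this is (0.2564 + 0.4662 + 0.378)/40 = 0.0275, so the standard error is 0.166. Then |ln 0.55|/0.166 = 0.598/0.166 = 3.60, and 3.60 − 1.96 = 1.64, which gives 95% power. So k of about 0.19 reproduces the stated figure (up to about 0.25 with other variance forms).

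**2. Power.** About 40 attenders per arm give the planned 95% at that dispersion. Take 25% loss before month 3, half of the non-attenders with 1 calendar month and half with 2, and k = 0.2. Adding those months raises power from 94.9% to 97.6%. The time at issue would be 40.5 × 1.5 = 60.8 of 425.3 person-months (14%). At 12.5% loss it would be 20.25 × 1.5 = 30.4 of 455.6 (7%). All of this assumes that the calendars were returned.

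**3. Bias from analysing completers only.** Assumptions, none from the documents:
- Individual fall risk follows a gamma distribution with mean 1 and variance k.
- One arm loses 35% of its higher-risk half and 15% of its lower-risk half (25% overall). The other arm loses 25% at random.
- The true IRR is 1.00.

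The mean risks of the higher and lower halves are 1.385 and 0.615 at k = 0.25, and 1.857 and 0.143 at k = 2. The rate in that arm's completers, relative to truth, is:
- k = 0.25: (0.65 × 1.385 + 0.85 × 0.615)/1.50 = 0.95
- k = 2: (0.65 × 1.857 + 0.85 × 0.143)/1.50 = 0.89 (one simulation of the same set-up gave 0.88)

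The other arm stays at 1.00, so these are the IRRs. With half the loss (17.5% and 7.5%):
- k = 0.25: (0.825 × 1.385 + 0.925 × 0.615)/1.75 = 0.98
- k = 2: (0.825 × 1.857 + 0.925 × 0.143)/1.75 = 0.95

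If both arms lose participants in the same pattern, the IRR stays at 1.00.

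**4. The same case with partial follow-up.** If leavers contribute 1 month on average, the higher-risk half supplies 0.65 × 3 + 0.35 × 1 = 2.30 and the lower-risk half 0.85 × 3 + 0.15 × 1 = 2.70 person-months per head. The pooled rate is:
- k = 0.25: (2.30 × 1.385 + 2.70 × 0.615)/5.00 = 0.97
- k = 2: (2.30 × 1.857 + 2.70 × 0.143)/5.00 = 0.93

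With 1.5 months on average the weights are 2.475 and 2.775, and the results are 0.98 and 0.95. The bias shrinks but remains.

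**5. Missing calendars among attenders.** Assume that 20% of one arm and 5% of the other lack one of three calendars at random. If the full exam offset is kept with only the reported falls, a true 1.00 reads (1 − 0.20/3)/(1 − 0.05/3) = 0.949, or 1.054 with the arms reversed. In simulation (54 per arm) type I error was 6–7%. With 10% missing in both arms the IRR is 1.00.

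If calendars instead go unreturned only for fall-free months, the exam offset is unbiased. In simulation the calendar offset then gave 1.05 (k = 0.2) or 1.04 (k = 1), and 0.95 or 0.96 with the arms reversed.

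**The case against.** - **The plan does not say that non-attenders are excluded.** This is true, and a reader should not infer a stated exclusion. The phrase person-months of follow-up could be stretched to mean months observed. Against that, the same sentence bounds the time by the two exams, and the next expects only slight variation around 3 months. What stands is that t_i is undefined for non-attenders and that exclusion is the literal consequence.
- **Collected data may not be lost.** A reader might infer that calendars in hand will be discarded. The documents do not support this: with no return schedule given, calendars could be collected at the 3-month exam, and non-attenders would then have none in hand.
- **Power is already budgeted.** A reader might infer a power shortfall. There is none against the plan's target, because 40 finishers per group is what it sized for. Larger values of k lower power, but they do not fit the plan's 40 per group whatever offset is used. That is a separate question.
- **Missing calendars need not bias the IRR.** A reader might infer that a missing calendar is scored as no falls and favours one arm. That requires an unrecovered calendar, the full exam offset and unequal return by arm, none of which the documents show. At 10% against 5% the IRR is 0.9667/0.9833 = 0.98.
- **The remedy can err too.** This stands: step 5 shows an error of similar size if fall-free months are the ones not returned. Hence the sensitivity analysis.

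**Conclusion.** The concern holds as a gap in the primary analysis that should be closed before the data are analysed. Section 8 defines exposure in a way that fits only 3-month attenders, and nothing elsewhere supplies a rule for anyone else.

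The main risk is bias from leaving out randomized participants whose dropout may be related to falls. In the assumed case a true IRR of 1.00 reads about 0.95 at k = 0.25, the value close to the plan's own figures. It reads about 0.89 at k = 2, a dispersion that those figures do not fit. Both rest on 25% loss before month 3, which is an upper-end use of a whole-protocol figure, and on a risk-related pattern in one arm only. Half the loss roughly halves the bias, and the same pattern in both arms removes it. The direction cannot be predicted from the documents.

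The missing-calendar point is secondary: the rule is absent, but bias in the IRR depends on unequal return by arm and on keeping the full exam offset. Confidence is medium, because loss before month 3, calendar return and dispersion are all unstated.

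**What to change.** In section 8:
- Include every randomized participant with any calendar data.
- Define t_i as the person-months for which falls were ascertained, from baseline to the 3-month exam or the last calendar, whichever is earlier. Count FALLS_i over exactly that time.
- State in advance whether a month recovered at the exam counts as ascertained.
- Report, by arm, calendar coverage, loss before month 3, and the number with no calendar data.
- Add two sensitivity analyses: (a) 3-month exam attenders only, with the exam-to-exam offset; (b) unreturned months scored as fall-free.

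The cost is a few sentences, one derived coverage variable and two extra model fits, with no new data collection. The price is an assumption: the main analysis then relies on data being missing at random given arm and covariates. It reduces but does not remove bias from fall-related dropout, and it can itself be biased if calendars go unreturned because nothing happened. Analysis (b) checks that case.

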STUDY PROTOCOL

Principal Investigator: [name]

[contact]

E-mail: [contact]

ClinicalTrials.gov number: NCT03972969

Protocol date: 3/16/2022

1. Aims/Objectives

A meta-analysis indicates that falls are very common in Parkinson's disease (PD), even within a brief period of 3 months, when about half of patients will sustain at least 1 fall (Pickering et al., 2007). Randomized, controlled trials (RCT) have examined the effects of exercise interventions on reducing falls in this population; however, with mixed results. The goal of the proposed research is to evaluate two approaches to implementing an exercise program: 1) an in-person exercise program that demonstrated a significant decline in fall rates over time in a small sample of patients (Sparrow et al., 2016) and 2) a home-based program centered around remote, exercise instruction.

In the proposed RCT, 162 VA patients with PD will be randomly assigned to one of three 3-month interventions: in-person exercise, remotely-delivered exercise, or health education. Fall rates will be compared between each exercise intervention group and the health education group.

2. Background Information

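### Does the in-person versus remote test need its own aim and sample size when the trial was sized only for comparisons with control?

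*Combined protocol and SAP*

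**What the plan says.** Section 1 states the planned analysis as two comparisons with control: "Fall rates will be compared between each exercise intervention group and the health education group". Section 3 adds a claim of novelty, that to the authors' knowledge "this will be the first RCT to compare a remotely-delivered program with an in-person program on reducing fall rate in patients with PD".

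Section 8 opens with three comparisons: fall rates "will be compared between each intervention group and the control group and between the two intervention groups". It then singles out b1 and b2 (each exercise group against control) as the coefficients that matter for comparing groups. After those it adds that "the linear contrast b1-b2 will be tested to compare the fall rates between the in-person intervention and the remotely-delivered intervention", with exp(b1-b2) as the estimated incidence rate ratio.

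Section 8.1 sets 40 per group for 95% power "to detect a between-group difference in fall rate of 45% for a specific exercise group vs. the control group". It names both control comparisons in parentheses, "each at a two-sided significance level of 0.05". It gives no target difference, power or margin for b1-b2. No section says that a non-significant b1-b2 will be taken to mean that the two programs are equally good.

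**The concern.** The comparison that Section 3 presents as new is tested, but it is missing from the aim and from the sample-size statement. Nor does the sample size carry over to it. If in-person just meets the 45% target, its rate is 45% below remote's only when remote does nothing, so any useful remote effect leaves a gap smaller than the one the trial was sized to detect.

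What would be at stake is the reading of a null result. Section 3 argues for remote delivery on grounds of access, so readers will look at b1-b2. A non-significant test might be taken as evidence that remote is as good when half the benefit had been lost.

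**Working it through.** **Inputs.** From Section 8.1: control rate 1.3 falls per person-month, target reduction 45%, 40 per group, two-sided 0.05, stated power 95%. From Section 8: about 3 months of follow-up, so 1.3 × 3 = 3.9 expected control falls. From Section 1: 162 randomised, or 54 per group if allocation is equal (the ratio is not stated). Assumed: the dispersion k, which the plan does not give, and a two-sided 0.05 level for b1-b2.

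**Formula.** For mean counts m1 and m2 with n per group, SE of the log rate ratio = √[(1/m1 + 1/m2 + 2k)/n]; z = |log(m1/m2)|/SE; power = Φ(z − 1.96) + Φ(−z − 1.96).

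**The plan's own figure.** In-person mean 3.9 × 0.55 = 2.145; control mean 3.9; log ratio −0.598. With k = 0.189 and n = 40, SE = √[(0.466 + 0.256 + 0.378)/40] = 0.166, z = 3.60, power 95%. So the stated 95% implies k of about 0.19. At k = 1 the same comparison has 63% power.

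**b1-b2 with half the benefit lost.** Remote at −22.5% has mean 3.9 × 0.775 = 3.0225; log ratio −0.343. With k = 0.189 and n = 40, SE = √[(0.466 + 0.331 + 0.378)/40] = 0.171, z = 2.00, power 52%.

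| Reduction, in-person / remote | n per group | k = 0.19 | k = 1 |
|---|---|---|---|
| 45% / 22.5% | 40 | 52% | 25% |
| 45% / 22.5% | 54 | 64% | 33% |
| 61% / 30.5% | 40 | 87% | 56% |
| 67% / 33.5% | 40 | 95% | 70% |

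Simulating the three-arm negative binomial model (3,000 runs per setting) for the 45% / 22.5% case gave 54% and 28% at n = 40, and 65% and 34% at n = 54.

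**Detectable gap.** With in-person at −45%, n = 40 and k = 0.19, 80% power needs a remote rate 0.882 times control, a remote/in-person ratio of 0.882/0.55 = 1.60. Remote would then cut falls by about 12%.

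**Precision if the two programs are equal.** With both means 2.145 and n = 40, SE = 0.181 at k = 0.19 and 0.271 at k = 1. The expected 95% interval for exp(b1-b2) is 0.70 to 1.43, or 0.59 to 1.70.

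**Size needed if this were a main aim.** For 80% power at 45% versus 22.5%, n = (1.96 + 0.8416)² × (0.466 + 0.331 + 2k)/0.343², about 79 analysed per group at k = 0.19 and 187 at k = 1.

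**The case for a change.** The strongest case for acting is that a contrast advertised as a first has no stated status or precision, is close to a coin-flip at the plan's own design effect and implied dispersion, and could be labelled in a few sentences at almost no cost. The arithmetic behind this stands, and so does the warning that a non-significant b1-b2 would not show equal benefit: the interval of 0.70 to 1.43 makes that plain.

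The step from there to a required change does not stand, for four reasons.

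- The order of importance can already be read from the plan. Sections 1 and 8.1 name the same two comparisons, and Section 8 puts b1 and b2 first. A subordinate contrast without its own power calculation is ordinary practice.
- The equivalence reading is not in the plan, so a caveat would rebut a claim nobody has made.
- The low end of the power range rests on k = 1, which has no source in the documents. At k = 1 the control comparisons would have 63% power rather than 95%; that would be a question about the unstated dispersion, not about this contrast.
- Losing half the benefit, starting from a 45% effect, is a scenario brought in by the review. Section 8.1 treats 45% as the smallest effect of interest, below the cited 61% and 67%. The 40 per group may also be cautious, since the 25% loss refers to completing the whole protocol, which has a 6-month assessment, while falls are analysed over 3 months.

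**Conclusion.** No change to the plan is needed. The test of b1-b2 is a subordinate contrast with limited precision, and no stated figure or rule is wrong. Its power for a 45% versus 22.5% reduction is about 52% with 40 per group and 64% with 54. This assumes k of about 0.19 (back-solved from the plan's 95%), 3 months of follow-up, two-sided 0.05 and no covariate adjustment.

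An analyst would normally report exp(b1-b2) with its confidence interval, describe it as secondary and not read non-significance as equivalence. Writing that into the plan would be harmless, but it would alter neither the data, the model, the test nor the control comparisons. Sizing for the contrast would mean about 79 to 187 analysed per group (k = 0.19 to 1) instead of 40, to secure a power the trial never promised.
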